## **15. Withdrawal of Subjects**

Anticipated circumstances where subjects may be withdrawn from the research without their consent may be if their pain scores worsen for longer than a week.

In the event of early withdrawal, patients will be tapered from 0.5 (if currently taking that dosage) to 0.250 for 1 week. However, according to the manufacturer's (Boehringer Ingelheim, Inc) packet information, pramipexole at doses of up to 0.75 once daily can be discontinued without taper.

While there are no contraindications associated with pramipexole, the collection and reporting of adverse are as follows:

The collection and reporting of adverse events will occur at: (1) the time of the phone conversation at the end of weeks 1 and 3 with the CRC who will collect the Brief Pain Inventory scores, (2) at the end of week 2, the time of the mid-term in-person meeting with the CRC when the subject will provide the scores of the BPI for that week and will pick up drug dispense #2, (3) At the final in-person with the CRC, at the termination of the study at week 4, and (4) at any point during the study when the subject calls the CRC to report an adverse event or when the subject calls [name]. All adverse events will be recorded by the CRC and kept with the subject's study records.

See actions upon evidence of symptomatic orthostatic hypotension above (Section 14, "Provisions to monitor the data to ensure the safety of subjects"), and other adverse

reactions will be monitored during dose escalation during weeks 1-2, as well as throughout the 4-week study. Monitored will occur as detailed in “Collection and Reporting of Adverse Events”.

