### **5. Number of Subjects**

- 5.4. All subjects will be recruited from the UNMH outpatient population from the UNMH Pain Center.
- 5.5. The target sample size is 30 subjects with complete data. The investigators may recruit up to 45 patients to allow for any dropouts.
- 5.6. All subject recruited will participate. There will be no screening after recruitment.

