## **7. Study Endpoints**

- 7.4. The primary endpoint is the paper-and-pencil survey, the Brief Pain Inventory. The secondary study endpoints will be mRNA and protein analysis from blood samples provided at the initiation and terminal of the study.
- 7.5. *Safety endpoints of the study will include the following: (1) Worsening of pain score or increased verbal dissatisfaction with pain relief, (2) sudden onset of sleep without warning, (3) intense urges, (4) hallucinations and/or psychotic-like behaviors, (5) fever, and (6) orthostatic hypotension. While the patients who experience these adverse events, dosing with pramipexole will require a 50% step-wise reduction over a period of two weeks. Given the maximal allowable dose is 0.75 mg, this prescribed step-wise reduction is well within the manufacturer's recommended tapering of pramipexole, which the recommended dose reduction is 0.375 per day.*
- 7.6. No exploratory endpoint are in the current study.

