## **12. Study Procedures**

The goal of Phase II will be to determine the therapeutic benefit of pramipexole for pain, which is a repurposing of this FDA-approved drug with a good safety profile. In collaboration with [name] (co-I at UNMH Pain Clinic), patients from the UNM pain clinic will be recruited who are experiencing modest or suboptimal pain relief. The patient will meet the CTSC Clinical Research Coordinator, who will escort the patient to the Clinical Research Lab. At the time, an explanation of the study, consent, the Brief Pain Inventory survey will be completed, blood draw and Clinocard will be given to the patient (\$15/visit). Scheduling for the midterm visit to the CTSC (at the end of two weeks) will be determined. At the time of consent, all patients will be under standard pain treatment and will be randomized into two groups: (1) patients receiving pramipexole in addition to their standard ongoing pain treatment, or (2) no pramipexole but will continue to receive the standard pain treatment. Patients will be followed up in the morning at weekly intervals to provide pain scores either by phone (for week 1 and 3), or by return visit (for end of week 2 and at the end of week 4) until study termination which is at the end of week 4.. At the initiation of the study and at the end of 4 weeks, blood will be collected and analyzed for mRNA for TLR4, p38, NFKB, NLRP3-ASC, Caspase-1, IL-1 $\beta$ , TNF- $\alpha$ , HMGB1, and IL-10. The dose and route of administration of pramipexole will be identical to that previously approved for the treatment of Restless Legs Syndrome and according to manufacturer's recommended prescribing protocol (Mirapex, Boehringer Ingelheim Int. GmbH). Briefly, oral dosage will be titrated each week to achieve a weekly total daily dose of 0.125 (mg), 0.250, 0.5 or 0.750. Patients will take one capsule containing pramipexole or placebo 2-3 hours before bedtime.

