Patient recruitment, assessment of Brief Pain Inventory (BPI): Pain scores and blood draws will be conducted at the CTSC Participant Clinical Interactions Unit with the CTSC Clinical Research Coordinator. Blood samples collected by the CTSC Clinical Research Coordinator will be analyzed at the Center for Molecular Discovery by personnel from [name] lab, trained by personnel from the Center for Molecular Drug Discovery (Director; [name], co-I). Personnel from the [name] lab have expertise in inflammatory marker analysis from PBMCs [57, 58]. All freshly collected blood samples will be frozen and stored by the Clinical Research Coordinator at the CTSC Clinical Laboratory and will be transported to the Center for Molecular Drug Discovery once ALL of the samples for the study (all 30 patients) have been collected. This is to allow for assay to be conducted at the same time to avoid potential effect of 'time of assay' that may impact data.

All subjects will therefore meet with the CTSC Clinical Research Coordinator for a total of 3 times; at the initiation of the study, at mid-term when the second batch of drug is dispensed and unused drug is returned, and at termination for a second and final blood draw and providing all completed Brief Pain Inventory surveys (5/patient). At the termination of the study, patients will turn in their paper copies of the Brief Pain Inventory questionnaire completed for each week of the study (total 4 weeks). Original data records are important to demonstrate all necessary physical documentation of the study.

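### Section 15 lets worsening pain end a subject's participation without saying whether week-4 BPI and blood are still obtained, so the outcome can decide who has week-4 data

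*Combined protocol and SAP*

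**What the plan says.** Section 15 (Withdrawal of Subjects) says subjects "may be withdrawn from the research without their consent may be if their pain scores worsen for longer than a week". Section 24 (Consent Process) adds that investigators may end participation in the interest of the subject or of the study. Section 7.4 states: "The primary endpoint is the paper-and-pencil survey, the Brief Pain Inventory". The withdrawal trigger and the primary outcome are thus the same kind of measurement.

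For what follows, Section 15 gives a taper ("In the event of early withdrawal, patients will be tapered") and then repeats the adverse-event contact schedule from Section 14. That schedule mentions BPI collection by phone at weeks 1 and 3, the week-2 visit and the final visit. It does not say that withdrawn subjects stay on it, and it does not mention blood.

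Section 12 sets the data schedule: "At the initiation of the study and at the end of 4 weeks, blood will be collected and analyzed for mRNA". Subjects meet the coordinator for the last time "at termination for a second and final blood draw and providing all completed Brief Pain Inventory surveys (5/patient". Section 5.5 sets the target: "The target sample size is 30 subjects with complete data. The investigators may recruit up to 45 patients to allow for any dropouts".

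Section 13 names a statistical test for the cell experiment only. It gives no analysis set, model or missing-data method for the clinical phase.

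**The concern.** If a subject leaves the research because pain has worsened, and nothing more is collected, the absence of a week-4 value is itself a result of the outcome. Randomization makes the arms comparable only while all randomized subjects can be compared. A target counted in subjects with complete data, with room to recruit more, lets withdrawn subjects be replaced instead of followed.

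For BPI the loss is partial, because scores already given by phone or at the week-2 visit are on record. For blood it is total. There are two samples, the second belongs to the termination visit, and no interim sample exists to work from.

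**Working it through.** **Timing.** Pain is scored weekly. Worse for longer than a week can be read loosely as two successive worse scores, met at week 2 at the earliest, or strictly as three, met at week 3. What then remains is the week-3 call and week-4 visit (loose), or the week-4 visit alone (strict). Withdrawal before week 4 without that visit loses 1 of 2 blood samples.

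**The plan's own figures.** (45 − 30)/45 = 33%, so up to 15 recruited subjects may lack complete data. No dropout rate is stated.

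**Illustration.** None of these inputs is in the documents. Scores at baseline and weeks 1–4 have SD 2 and equal correlation r of 0.5 or 0.7. Placebo has no mean change. Worsening means 0.5, 1 or 2 points above baseline. Every subject meeting the rule is withdrawn unless stated. Titration is ignored. There are 1,000,000 simulated subjects per arm. The table gives the week-4 benefit seen in completers.

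| Setting | Two-score rule | Three-score rule |
|---|---|---|
| Placebo subjects withdrawn | 5–31% | 1.5–17% |
| Same effect in all, true 1.5 | 1.13–1.44 | 1.24–1.48 |
| Same, half of those meeting the rule withdrawn | 1.36–1.47 | 1.38–1.49 |
| Same effect in all, true 3 (the Section 12 goal) | 2.46–2.92 | 2.67–2.97 |
| Same effect in all, true 0 | no bias | no bias |

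The direction changes when responses differ between subjects. I kept the mean benefit at 1.5 and let a minority of active subjects worsen, with immediate onset:
- 20% worsen by 2 and the rest improve by 2.375 (0.8 × 2.375 − 0.2 × 2 = 1.5). Completers show 1.68–1.87 under the two-score rule.
- 30% worsen by 1.5 and the rest improve by 2.79 (0.7 × 2.79 − 0.3 × 1.5 ≈ 1.5). Completers show 1.74–2.00 under the two-score rule.
- Over both mixes and both rules the range is 1.66–2.00.
- With mean effect zero, half improving and half worsening by 1.5, completers show a false benefit of 0.20–0.66 over both rules.

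**Scale.** At 15 per arm (1:1 assumed), the SE of the difference in change is 2 × √(2(1 − r)) × √(2/15), which is 0.73 for r = 0.5 and 0.57 for r = 0.7. The largest understatement is 1.5 − 1.13 = 0.37 (r = 0.5) or 1.5 − 1.18 = 0.32 (r = 0.7), about half an SE. The 0.66 arises at r = 0.7. There the variance of change is 2 × 4 × 0.3 = 2.4, and the mixed responses add 1.5² = 2.25 in the active arm. The SE is then √((2.4 + 4.65)/15) = 0.69, so the false benefit is about one SE.

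**What continued collection gives (same effect in all, true 1.5).**
- Full follow-up gives 1.50 if the effect persists after stopping. If it ends on stopping, follow-up gives 1.36–1.50 with immediate onset and 1.23–1.50 with gradual onset. At the low end of the latter, completers give 1.29.
- An analysis of all recorded BPI scores, without follow-up, gives 1.50 if withdrawal depends on those scores only. If discretion also tracks unrecorded pain, the worst case is 1.24–1.48 (two scores) or 1.39–1.50 (three).
- Blood, true 0.5 SD, correlation 0.3–0.5 with BPI change: completers 0.40–0.50. Follow-up gives 0.50 if the effect persists and 0.41–0.50 if it ends.

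**The case against.** The strongest reply is that Section 15 itself repeats a contact schedule that names BPI collection and the final visit, and that Section 12 follows patients to week 4 with no stated exception. That is fair, and it rules out saying that collection is forbidden after withdrawal. But the list is the general adverse-event schedule, sits beside text about leaving the research, and omits blood. It leaves the question open.

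Second, the rule is discretionary, so the rates above are worst cases. This stands: if half of those meeting the rule are withdrawn, the same-effect bias falls to 0.03–0.14 (two scores) or 0.01–0.12 (three). The 15 of 45 is recruitment headroom for any dropout, not an expected withdrawal rate.

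Third, follow-up may recover little. The documents lean that way: Section 2.2 reports that allodynia in mice returned by 24 hours, and Potential Risks gives a half-life of 8.5 to 12 hours. If the effect ends on stopping, follow-up can land no nearer the on-drug effect than completers do. This also stands. What follow-up secures is a comparison of the groups as randomized.

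Fourth, no completer analysis is stated. That is true, but nothing rules it out, and complete data is what Section 5.5 counts.

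**Conclusion.** The concern holds. As written, the outcome can determine who has week-4 BPI and blood, and no passage assures collection after withdrawal. It should be fixed, although the likely bias is modest against the precision of 15 per arm.

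A reader might infer that a true benefit will be understated. The documents do not support one direction. Understatement (1.13–1.48 of 1.5) follows if everyone has the same effect. Section 9 anticipates improvement, no change or worsening; if some active subjects worsen and are removed, benefit is overstated (about 1.7–2.0 of 1.5) or can appear when the mean effect is zero. If the drug affects no one and the rule is applied alike in both arms, no between-arm bias arises.

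All these sizes rest on assumed SD, correlation, threshold and use of the rule. Week 4 as the main BPI time point is inferred from the schedule. No conclusion on power is drawn.

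**What to change.** In Section 15, and consistently in Section 24, state that stopping study drug does not end participation. Unless the subject declines, the scheduled weekly BPI contacts continue, the week-4 BPI and blood draw are requested, forms completed so far are collected, and the date and reason for stopping are recorded. The decision to stop drug stays with the physician, as in Section 9.5.

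In Section 13, compare all randomized subjects in their assigned arms using all recorded BPI scores with baseline (for example a repeated-measures mixed model) and all available blood samples, with completers as a sensitivity analysis only. Say whether week-4 data obtained after stopping belong to the main comparison.

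Section 7.5 answers worsening pain, among other events, with a dose change ("dosing with pramipexole will require a 50% step-wise reduction over a period of two weeks"), while Section 15 allows withdrawal. These may be sequential, but the text does not say so, and the passages must be reconciled. No clinical rule is proposed here.

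**Cost.** Per withdrawn subject, at most the week-3 call and the week-4 visit, both already scheduled, with $15 for the visit. If 45 are recruited, up to 45 × 2 = 90 samples are assayed instead of 30 × 2 = 60, which matters in a study that Funding describes as unfunded. In the illustration, scores after stopping dilute a pure on-drug estimate by up to 1.50 − 1.23 = 0.27 points.

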## **16. Data Management/Confidentiality**

- 16.4. Data will be shared only among the study team members. Data will not be shared to an external source.
- 16.5. To minimize potential breach of confidentiality, all electronic data will be maintained in a password-protected database to which only CTSC study staff with a legitimate need will have access. All paper documentation will be kept in a secure file cabinet in a locked office in the CTSC or in Drs. [name] or [name]’s office at UNMH.

## **17. Data and Specimen Banking**

Blood samples will be banked locally only for the study period. All unused blood samples will be destroyed at the termination date of the study, which is 1 year after the study period begins.

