### **6. Study Timelines**

#### *6.4. Describe:*

- The duration the subject will participate in the study is 4 weeks
- The duration anticipated to enroll all subjects may require 10-11 months
- The expected duration for the investigators to complete the study analyses will be 12 months, with most of the analysis occurring in the final months 11-12.

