## **9. Resources Available**

- 9.4. The PI and study staff have received training for clinical trials. [name] (PhD) is a basic scientist conducting the cell assays and interpreting the data results. [name](PhD) is a basic scientist directing the CTSC core for conducting the cell assays and interpreting the resultant data. [name] (PhD) is a statistician and familiar with clinical trials designs, and [name] (MD) is a physician who specialized in pain treatment at the UNMH Pain Clinic.
- 9.5. [name], MD will be responsible for medical decision-making and ordering and evaluation of necessary diagnostics and therapeutics.
- 9.6. [name] treats 15-30 patients daily at the UNMH Pain Clinic. With this high access to patients, the goal of enrolling 30 patients during an 11 month period is predicted to be very feasible.

All 30 recruited patients will be needed with no further screening.

An estimated 6 hrs per patient will be devoted to consent, completing surveys, blood draw, scheduling and dispensing the pramipexole or placebo by the Clinical Research Coordinator.

- The facilities used will be at the CTSC where consent, enrollment, scheduling visits, obtaining blood samples, completion of the Brief Pain Inventory survey, dispensing drugs at initiation and at midterm (end of week 2,) and collecting unused drug at termination. For the biological assays from human cell lines or from blood samples, the clinical laboratory arm of the CTSC, Center for Molecular Drug Discovery, will be used.
- The availability of medical and/or psychological resources that subjects might need as a result of an anticipated consequences of the human research will be available by [name] or by referral from [name]. The anticipated consequences of the research will be (1) improved pain relief, (2) no change in pain relief, or (3) a worsening of pain. [name] will continue to monitor patients after the study is terminated, as these patients will continue to receive outpatient care from the pain clinic.

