## **27. Sharing Study Progress or Results with Subjects**

27.4. The design of the study will not allow for results to be shared with the subjects during the course of study. In addition, all of the blood samples will not be analyzed until after all subjects have completed the study. A summary of the study results will be disclosed at the study termination (end of month 12) via written communication and a copy of the manuscript submitted for peer review in a science journal.

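### Blood samples wait for one batch assay after the last patient, but the one-year destruction date leaves about 33 days at 10 months' enrolment and 0 to 3 days at 11

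*Combined protocol and SAP*

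**What the plan says.** All of this is in the combined protocol and SAP.

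- **Enrolment (Section 6, Study Timelines):** "The duration anticipated to enroll all subjects may require 10-11 months". Section 9 (Resources Available) uses the upper figure: "the goal of enrolling 30 patients during an 11 month period is predicted to be very feasible".
- **Follow-up (Section 6):** "The duration the subject will participate in the study is 4 weeks".
- **Blood draws (Section 12, Study Procedures):** "At the initiation of the study and at the end of 4 weeks, blood will be collected and analyzed for mRNA". Each patient therefore gives two samples, the second on leaving the study.
- **Single batch (Section 12):** the frozen samples "will be transported to the Center for Molecular Drug Discovery once ALL of the samples for the study (all 30 patients) have been collected". The stated reason is to avoid a time-of-assay effect. Section 27 repeats the rule: "all of the blood samples will not be analyzed until after all subjects have completed the study".
- **Destruction (Section 17, Data and Specimen Banking):** banking is local and lasts only for the study period, and then "All unused blood samples will be destroyed at the termination date of the study, which is 1 year after the study period begins".

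Section 8 adds that blood is stored for assay when the project period terminates. Section 7 makes the mRNA and protein results the secondary endpoints and the Brief Pain Inventory the primary one.

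**The concern.** The batch rule fixes the earliest date on which any sample can be assayed: after the last patient's week-4 draw. Section 17 fixes the latest date on which an unused sample may exist: one year from the start of the study period. The time between the two depends on how long enrolment takes, and the plan's own upper figure uses up nearly all of it. I find no provision for extending storage.

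Sections 8 and 17 add to the difficulty. One places the assay at the termination of the project period. The other places destruction at the termination of the study. If these are the same date, the order of the two steps is not stated.

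At stake are the secondary endpoints or, more modestly, the ability to repeat an assay that fails. Nothing here touches the pain scores.

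**Working it through.** The documents give no figure for the assay window, so there is none to reproduce. The check is calendar arithmetic.

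**Inputs from the plan**
- Enrolment: 10 to 11 months (Section 6); 11 months for 30 patients (Section 9).
- Last draw: 28 days after the last enrolment (Sections 6 and 12).
- Destruction: 12 months after the study period begins (Section 17).
- Samples: 30 patients × 2 draws = 60. Section 12 lists nine mRNA targets, and Section 7 adds protein.

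**Assumptions**
- The study period begins at first enrolment (varied below).
- An average month is 365/12 = 30.42 days.

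**Formula:** days left = 365 − (enrolment months × 365/12) − 28.

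| Enrolment | Calculation | Days left | Exact calendar months |
|---|---|---|---|
| 10 months | 365 − 304.2 − 28 | 32.8 | 31 to 34 |
| 10.5 months | 365 − 319.4 − 28 | 17.6 | not run |
| 11 months | 365 − 334.6 − 28 | 2.4 | 0 to 3 |

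The last column repeats the count with real calendar months over start dates in 2018 to 2020. The spread comes from differing month lengths, so 0 to 3 days is a fairer statement than 2.4.

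**If the study period starts before first enrolment** (assumed lags, subtracted from the days left):

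| Lag | 10 months | 10.5 months | 11 months |
|---|---|---|---|
| 7 days | 25.8 | 10.6 | −4.6 |
| 14 days | 18.8 | 3.6 | −11.6 |
| 30 days | 2.8 | −12.4 | −27.6 |

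**If replacements are enrolled after the stated period.** Section 5 allows up to 45 recruits to reach 30 with complete data. At a constant 30 patients in 11 months (an assumption about the rate), each extra patient adds 334.6/30 = 11.2 days. That exceeds the 2.4 days left, so one replacement would put the last draw past the destruction date. At 30 in 10 months, each adds 304.2/30 = 10.1 days, and 32.8 days would cover about three.

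**How early enrolment would have to end.** The assay duration is not given, so I show a range. Latest enrolment = (365 − 28 − assay days) ÷ 30.42.
- 14 days: 323/30.42 = 10.6 months.
- 30 days: 307/30.42 = 10.1 months.
- 60 days: 277/30.42 = 9.1 months.

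Only the first two fall within the stated 10 to 11 months, and the 30-day case barely does. Section 27 also places the results summary at the end of month 12, so analysis and reporting must share the same window.

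**The case against.** The strongest reply is that *unused* in a banking section ordinarily means what is left after the planned assays. Section 8 fits this, because it treats assay as the planned use of the stored blood at the end of the project. On that reading no endpoint data are lost, and only spare material goes. This is a fair reading and may be what was intended. But Section 17 does not say so, a sample not yet assayed is literally unused, and the section separately limits all banking to the study period. Even on the milder reading, material for a repeat run is gone on the fixed date, although the documents do not mention repeat runs.

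A second reply is that Section 17 names the study's termination, and that the one-year figure is only its expected date, which would move if enrolment overran. No section says that it would move, and Section 27 also puts termination at the end of month 12.

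A third is that 11 months is the top of a hedged estimate. This stands: at 10 months there are about 33 days, and the plan is not unworkable across its range. Section 6 places most of the analysis in months 11 to 12, which suits the lower end.

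A reader might go further and infer that the batch cannot be assayed in time, or that the plan will lose its secondary endpoints. The documents do not support either. They give no assay duration, and the laboratory is a local unit of the same research centre, so transport is short. The team that would destroy the samples is also the one that needs them. Nor is it established that replacements add time, because the 10 to 11 months is for all subjects and may already include the allowance up to 45; Section 9, which ties 11 months to 30 patients, leaves this open.

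**Conclusion.** The stated rules fit together at the lower end of the enrolment estimate and leave almost no room at the upper end: about 33 days at 10 months and 0 to 3 days at 11, for about 60 samples. These figures assume that the study period begins at first enrolment. A start even a week earlier, or a replacement enrolled after month 11, would make the 11-month window negative.

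Whether a given window is long enough is a judgement, because the assay time is unknown. The consequence depends on how *unused* is read: literally, unassayed secondary-endpoint samples could have to be destroyed; as leftovers, only material for repeats is lost. This is a minor point about wording and timing, and it is worth correcting because doing so is cheap.

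**What to change.** In Section 17, replace the fixed date with an event. Samples are kept until the batch assay and any repeat runs are complete and the data are locked, and only the remainder is then destroyed. State an outer limit counted from the last blood draw, set with the laboratory's expected turnaround in mind. This also settles what *unused* means and the order of assay and destruction.

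Keep the single-batch assay; its rationale is sound and it is not the source of the problem.

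Section 25 says a tissue-banking consent form is attached. It was not available for this review, so check that its storage wording agrees and amend it only if it does not.

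The cost is a short edit to Section 17, possibly a matching consent change, and somewhat longer storage of the samples.
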